Transient acantholytic dermatosis (Grover's disease) is a rare skin disorder that presents most commonly as small, pruritic, erythematous papules on the trunk, particularly the central chest and back in males older than forty or fifty. The etiology is largely unknown, but the disease is thought to be associated with sweating and heat. The time course of Grover's disease is variable: some patients present with a self-limited two to four week eruption or a persistent non-resolving pattern. A clinical diagnosis can be made, but it is often confirmed through skin biopsy demonstrating typical features.¹

Psoriasis vulgaris is a common chronic inflammatory skin disorder that presents as erythematous, well-demarcated plaques with overlying silvery scale. It is associated numerous co-morbidities including obesity, cardiovascular disease, and autoimmune disease. Psoriasis is caused by the complex interactions of numerous inflammatory cells (T-cells and dendritic cells) and cytokines (TNF-alpha, Il-23, Il-12) that leads to abnormal differentiation in the epidermis, vascular dilation, and inflammatory cell recruitment.²

Blue light therapy in psoriasis has been studied in 2 randomized clinical trials, which have shown improvement in erythema and the LPSI score before and after therapy³⁻⁴. Although these studies studied the clinical response of psoriasis to blue light, neither examined histopathological or serological evidence of the immune system after blue light therapy. This study will also control for confounding variables such as 10% salicylic petroleum gel and moisturizers that were used in these two studies.

Standard of care treatment for Grover's disease include high potency topical steroids, application moisturizers, or emollients. Grover's disease patients may also minimize symptoms by avoiding triggers such as sweating or heat.

Standard of care for psoriasis include use of emollients, topical steroids, topical vitamin D, tar, calcineurin inhibitors, UV light phototherapy, and systemic therapies include methotrexate, retinoids, and biologic agents.

STUDY ENDPOINTS:

Objective 1 endpoint

- Recruitment of at least n=10 individuals with Grover's disease
- Recruitment of at least n=10 individuals with psoriasis vulgaris
- Demonstrate device safety as evidenced by absence of adverse events

STU#: STU00210472

- Demonstrate preliminary skin efficacy as demonstrated by clinical photo evaluation, patient reported outcomes with Dermatology Life Quality Index (DLQI) and skin histopathology with both Grover's disease and psoriasis vulgaris.
- Obtain user comfort and experience with phototherapy system using psychometric survey.

Objective 2 endpoint

- Elucidate keratinocyte and skin T-cell expression, and viability with blue light phototherapy
- Elucidate changes in circulatory T-cells based on flow cytometry and serum cytokines with blue light therapy.

STUDY INTERVENTION(S) / INVESTIGATIONAL AGENT(S):

The DUSA BLU-U (Model 4170) is a Blue Light Photodynamic Therapy Illuminator is intended to provide phototherapeutic light to the body. Blue light therapy is indicated for dermatological conditions such as actinic keratosis (AK) or inflammatory acne vulgaris. The BLU-U is approved by the FDA (K031805) as a Class II medical device. The BLU-U Illuminator to be used in this study is owned by the Northwestern Memorial Hospital Department of Dermatology and stored at the Dermatology Clinic in Chicago.

PROCEDURES INVOLVED:

Patients with Grover's Disease or Psoriasis vulgaris will be enrolled on the study.

In the informed consent process a Dermatologist will discuss Standard of Care treatment options for Grover's Disease or psoriasis vulgaris. If the patient wishes not to participate in this study the SOC treatment will be available to them. If the patient chooses to participate in this study, they may elect to do SOC treatment at any time (ending participation early) or after the phototherapy study visits are complete. Patients receiving SOC phototherapy (other light type, with activator creams, etc) may participate in this study by blocking a small site from their SOC phototherapy which will be treated with the Blue Light therapy in this trial. The Department of Dermatology has standard of care procedures for blocking specific sites during SOC phototherapy. These procedures will be followed if a patient that is enrolled on the study is simultaneously receiving SOC phototherapy for their condition. The clinical research team will consult with the phototherapy team for any patient that is receiving phototherapy.

No procedures in this study are standard of care for Grover's Disease or psoriasis vulgaris. If the symptoms of resolve before all phototherapy sessions are completed, the patient will have their final assessment and will have completed the study.

After informed consent a patient will be scheduled to start the study sessions immediately (if not on medications) or after a period of two weeks without using medications related to their skin condition. A site on the body will be identified for treatment with Blue Light, this will be the same site treated throughout the study.

The study visits will take approximately 30 minutes and will be done three times a week (at least 23 hours apart) over five weeks (15 visits total). Each session will consist of 16

STU#: STU00210472

minutes of Blue Light phototherapy with the BLU-U device over the affected area. Before starting the first, seventh and after the last session the patient will have a single, 6mm, punch biopsy of a characteristic lesion on the treated side only and a blood draw not exceeding 30 cc or two tablespoons in a visit. Tissue and blood, samples will be collected under the Dermatology Tissue Acquisition and Biorepository (IRB# STU00009443) protocol upon completion of the consent form for STU00009443.

During the first and last study visit the patient will be asked to complete surveys relating to their comfort and experience with the phototherapy symptoms and psychometric surveys of skin-related symptoms and skin-related quality of life.

In addition photographs will be taken of the afflicted areas before the first treatment, on the first visit, third visit after every 3 treatments until the end of the study as outlined in the table below.

Procedure Table

	Blue Light Phototherapy	Biopsy of lesional treated area	Blood Draw	Psychometric and Skin QoL survey	Photographs of afflicted skin area
Visit 0 - Consent					X
Visit 1 - Baseline	X	X	X	X	X
Visit 2	X				
Visit 3	X				X
Visit 4	X				
Visit 5	X				
Visit 6	X				X
Visit 7	X	X	X		
Visit 8	X				
Visit 9	X				X
Visit 10	X				
Visit 11	X				
Visit 12	X				X
Visit 13	X				
Visit 14	X				
Visit 15	X	X	X	X	X
Early completion (If condition resolved before final visit)	X	X	X	X	X

In this single arm, prospective clinical trial patients with Grover’s disease (n=10) will be invited to participate. A baseline biopsy of a characteristic lesion will be performed. Patients will be asked to complete a baseline psychometric survey of skin-related

STU#: STU00210472

symptoms and skin-related quality of life. Patients will then be asked to present to the phototherapy unit at Northwestern Dermatology for 15 total sessions of blue light therapy divided into 3 sessions a week for 5 weeks. The target irradiance is 14 mW/cm² with a total dose of 9 J/cm² requiring ~16 min per treatment. At each treatment session, clinical photos will be taken along with blue-light dosimeter readings at various locations of the body. At the mid-point of the study (7 sessions), an additional biopsy will be taken of a characteristic lesion. At the end-point of the study (15 sessions), a final biopsy will be taken of a characteristic lesion. If the lesion(s) is/are resolved a biopsy will be done adjacent to a previous biopsy. Patients will be asked to complete psychometric surveys relating to their comfort and experience with the phototherapy symptoms. In addition, they will complete psychometric surveys of skin-related symptoms and skin-related quality of life to compare against baseline. Subjects on the therapy will be asked to refrain from using systemic treatments throughout the trial with a 2-week washout period before the start of the trial. Topical treatments may be used, except in the area that is identified for treatment with Blue Light phototherapy provided by this study.

In a parallel single arm, prospective clinical trial patients with psoriasis vulgaris (n=10) will be invited to participate. A baseline biopsy of a characteristic lesion will be performed. Patients will be asked to complete a baseline psychometric survey of skin-related symptoms and skin-related quality of life. A baseline PASI-75 (a well-accepted clinical endpoint for psoriasis severity) will be conducted and across every treatment visit. Patients will then be asked to present to the phototherapy unit at Northwestern Dermatology for 15 total sessions of blue light therapy divided into 3 weekly sessions. The target irradiance is 14 mW/cm² with a total dose of 9 J/cm² requiring ~16 min per treatment. At each treatment session, clinical photos will be taken along with blue-light dosimeter readings at various locations of the body. At the mid-point of the study (7 sessions), an additional biopsy will be taken of a characteristic lesion. At the end-point of the study (15 sessions), a final biopsy will be taken of a characteristic lesion. Patients will be asked to complete psychometric surveys relating to their comfort and experience with the phototherapy symptoms. In addition, they will complete psychometric surveys of skin-related symptoms and skin-related quality of life to compare against baseline. A final PASI-75 will be scored. Subjects on the therapy will be asked to refrain from using any systemic treatments throughout the trial with a 2-week washout period before the start of the trial. Topical treatments may be used, except in the area that is identified for treatment with Blue Light phototherapy provided by this study.

In partnership with Northwestern University's Skin Biology Disease Research Center (one of only 6 in the country), all skin biopsy results will be processed for standard histology as well as immunohistochemistry. All biopsies will be stained for T-cell biomarkers including CD4, CD3, CD5, CD7, CD8 with cell populations counted for biopsies taken at baseline, at the midpoint and at completion of 15 sessions of blue light therapy. Keratinocyte apoptotic biomarkers will also be collected. Serological markers will be drawn both at baseline and after treatment from blue light in both the Grover's disease and psoriasis cohorts for immune-cell related cytokines (TNF- α , C-reactive protein, IL-6, E-selectin, and ICAM-1)

STU#: STU00210472

Procedures performed to lessen the probability or magnitude of risks:

Blue Light phototherapy sessions will be done in a private clinic room to maintain privacy of the patient. The researchers and patient will wear protective eyewear during use of the BLU-U device. Eyewear will block light with wavelengths of at least 500nm and shorter with an Optical Density (OD) of two or greater as recommended by the DUSA, the manufacturer of the BLU-U.

Photographs taken for the study will not include the full face and will exclude identifying marks such as tattoos. The intent of photographs is to document the efficacy of the treatment and any improvement of the disease.

Standard, sterile technique will be followed for both blood draws and punch biopsies.

Pictures of the psoriatic lesions and Grover's disease will be recorded and stored on research only devices (tablets/iPads). Those images will only be stored and accessed by research personal devices. The photographs will be used to assess whether the blue light therapy has improved the skins disease is psoriasis and Grover's disease.

DATA AND SPECIMEN BANKING

The biopsies and blood draws will not be stored for future use, and will be immediately used to histopathological examination and serological markers. Specimens will only be handled by the research team and the laboratory conducting pathological and histological testing. All research specimens will be labeled with a unique patient identifier, collection date and time.

Upon completion of consent, the biospy samples will also be shared with Dermatology Tissue Acquisition and Biorepository (IRB# STU00009443).

SHARING RESULTS WITH PARTICIPANTS

The results of the biopsies, and serological markers of the immune system will not be shared with the patient. At the end of the study a dermatologist will give an assessment of the patients condition and follow up care instructions if necessary.

STUDY TIMELINES

An individual will participate in the study for approximately 5 weeks. It will take approximately 1 year to enroll all study participates. The data to complete primary analyses is January 2021.

All recruiting will occur at either Northwestern Memorial Hospital (Arkes Pavilion in the outpatient dermatology offices).

INCLUSION AND EXCLUSION CRITERIA

Inclusion Criteria

1. Patient's aged 18-89 at time of enrollment
2. Previous diagnosis of psoriasis vulgaris or Grover's disease

STU#: STU00210472

3. All Groups: Subjects who are able and willing to give informed consent for this study and the Dermatology Tissue Acquisition and Biorepository (STU00009443).

Exclusion Criteria

1. All Groups: Subjects who are younger than 18 years of age or older than 90 years of age
2. Patients who receive systemic treatment within 2 weeks washout period before or during planned phototherapy
3. Patients using topical treatment on the area identified for treatment in this study
4. Patients prescribed any of the following drugs for issues not related to their psoriasis or Grover's disease
 - topical steroids
 - calcineurin inhibitors
 - methotrexate
 - retinoids
 - biologic agents
5. Unable to schedule phototherapy sessions
6. We will not recruit the following populations: adults unable to consent, individuals who are not yet adults (infants, children, teenagers), pregnant women, prisoners and other vulnerable populations.

RECRUITMENT METHODS

Patients will be recruited from the Department of Dermatology clinics at the time of their regular appointments and asked if they would like to learn more about this research study. We may also ask NMH Dermatologists to refer patients with psoriasis or Grover's disease or review medical records to search for eligible patients.

Eligible patients may be contacted by phone to gauge interest in the study and will be consented in person in the NMH Department of Dermatology.

An additional method of identifying patients will be through the Electronic Data Warehouse (EDW). The EDW at NU is updated daily. An algorithm can be set up based on the eligibility criteria of the trial to identify potential patients that have psoriasis or Grover's disease. Eligible patients will be sent an introductory email about the study and given 1 week or more to respond. If the team does not hear back from the patient or the patient does not respond indicating disinterest in the study, the clinical research team may follow up with a scripted phone call and schedule an appointment if the potential research subject is interested in the study.

Recruitment will be monitored carefully with weekly meetings of study coordinator and study PI. Barriers to recruitment will be identified and addressed to ensure recruitment remains on track.

COMPENSATION FOR PARTICIPATION IN RESEARCH ACTIVITIES

STU#: STU00210472

Subjects will be offered \$25 or \$50 USDs (payable via check) for their participation in each study visit involving Blue Light Therapy. Study visits involving blood draws and biopsies will pay \$50. All other visits will compensate \$25.

Total compensation that a patient can earn in this study is \$450 dollars.

WITHDRAWAL OF PARTICIPANTS

If the patient shows adverse signs from the blue light therapy, they will be withdrawn from the study. Participants will be free to withdraw from the study at any time. Participants may be withdrawn from the research without their consent if they are unable or unwilling to schedule and attend blue light phototherapy sessions.

RISKS TO PARTICIPANTS

Blue light: Hyperpigmentation has been a reported side effect of direct blue light therapy.

Biopsies: Present a small risk for scarring and infection

Blood draw: it might be uncomfortable, but there is otherwise very little risk

Photographs: Faces will be obscured, but there is a possibility that subjects may be able to be identified from the photographs that will be taken for the study.

Survey: Some questions may make patients uncomfortable or upset. Patients do not have to answer these questions if they do not want to.

Study procedure: As patients are asked to refrain from other skin treatments for two weeks before this study and during the study their symptoms may be worse. These conditions on the skin do not lead to long term sequelae when not treated for 1-2 months, but will be closely monitored during the study.

POTENTIAL BENEFITS TO PARTICIPANTS

The potential benefit is that blue light therapy may improve the clinical manifestation of Grover's disease and psoriasis.

DATA MANAGEMENT AND CONFIDENTIALITY

Subject identifiable medical information obtained as a result of this study is considered confidential and disclosure to third parties other than the principal investigator and the co-investigators is prohibited. All reports and communications relating to subjects in this study will refer to each subject only by their initials study identification number. Data generated as a result of this study are available to inspection on request by Food and Drug Administration or other government regulatory agency auditors, and the Northwestern University Institutional Review Board (IRB).

Subject identity will be protected through use of a coded list of identifiers, which will be maintained separately from the data set. Source documents and CRFs are kept in a

STU#: STU00210472

secured area (in a locked cabinet in a locked room) in the Department of Dermatology and all electronic data is password protected so that only authorized personnel can have access.

Photographs may be taken of the psoriatic lesions and Grover's lesions for research purposes only. Photographs will be labeled only by subject initials and identification number. All photos will be stored on a password protected server accessed by a password protected computer.

Data stored and used for future research will be de-identified. Data will not be used for future research outside of the scope of this study.

PROVISIONS TO MONITOR THE DATA TO ENSURE THE SAFETY OF PARTICIPANTS

This study is minimal risk.

PROVISIONS TO PROTECT THE PRIVACY INTERESTS OF PARTICIPANTS

Faces will not be photographed, but there is a possibility that subjects may be able to be identified from the photographs should there be identifying tattoos or marks. Areas with any identifying tattoos or marks will not be photographed.

This study is minimal risk.

COMPENSATION FOR RESEARCH-RELATED INJURY

This study is minimal risk. If a patient has complications or injury related to blood draw or biopsy, they will receive standard of care treatment to resolve their injury.

ECONOMIC BURDEN TO PARTICIPANTS

There are no costs to the participants involved in the study

CONSENT PROCESS

Prior to study entry, a written informed consent must be obtained from the subject. A copy of the signed consent form must be retained in the study file.

To protect participant confidentiality, we will conduct all research-related discussions and informed consent procedures in a private room. If a private room is not available, a designated area far enough away from other patients such that they cannot hear the conversation will be used. We will obtain written informed consent from the participant in English, using the IRB-approved consent form, prior to conducting any study procedure. The study procedures, risks, and benefits will be discussed and the study team will answer all questions prior to obtaining consent. All versions of the consent forms will be approved by the relevant ethics committees prior to study initiation.

Eligible participants who do not wish to participate in this study will continue to receive care according to local clinical standards

STU#: STU00210472

NON-ENGLISH SPEAKING PARTICIPANTS

Non-English speaking participants will not be included in this study.

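### Zero adverse events in 20 uncontrolled patients cannot demonstrate device safety, and no stated procedure would tell true absence from non-recording

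*Combined protocol and SAP*

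**What the plan says.** The STUDY ENDPOINTS section lists, for Objective 1, "Demonstrate device safety as evidenced by absence of adverse events". It gives no rate, threshold, interval or definition of an adverse event. The efficacy item that follows is worded more cautiously: "Demonstrate preliminary skin efficacy as demonstrated by clinical photo evaluation". The STUDY SUMMARY gives a sample size of 20, and PROCEDURES INVOLVED describes two parallel single-arm cohorts of 10.

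Several provisions touch on harm:

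- WITHDRAWAL OF PARTICIPANTS: "If the patient shows adverse signs from the blue light therapy, they will be withdrawn from the study".
- PROCEDURES INVOLVED, both cohort descriptions: "At each treatment session, clinical photos will be taken along with blue-light dosimeter readings at various locations of the body". In the psoriasis cohort a PASI assessment "will be conducted and across every treatment visit". At the first and last visits patients complete "surveys relating to their comfort and experience with the phototherapy symptoms".
- SHARING RESULTS WITH PARTICIPANTS: "At the end of the study a dermatologist will give an assessment of the patients condition".
- RISKS TO PARTICIPANTS names hyperpigmentation as a reported effect of the light, scarring and infection from biopsy, and possible worsening while other treatments are stopped. It promises close monitoring of the skin conditions.
- DATA MANAGEMENT AND CONFIDENTIALITY mentions source documents and CRFs without describing their content.
- QUALIFICATIONS TO CONDUCT RESEARCH makes a board-certified dermatologist responsible for oversight, including review of the patient's condition.

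The section on monitoring data for participant safety is one sentence, which classes the study as minimal risk.

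**The concern.** The endpoint turns a count of zero into a conclusion. Two things are wrong with that.

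First, the sample is too small. With 20 patients and no control, a device with a material event rate could easily show no events.

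Second, the count has no stated basis. Without a definition or a routine question, zero recorded events may mean that none occurred or that none were written down.

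The lack of a definition also cuts the other way. Patients have three punch biopsies, stop other treatments, and may have standard phototherapy elsewhere on the body: "Patients receiving SOC phototherapy (other light type, with activator creams, etc) may participate in this study by blocking a small site". Read literally, one event from any of these sources defeats the endpoint. Read as light-related events only, which the words on device safety and the withdrawal rule suggest, such an event can be set aside. Which reading applies could be settled after the data are seen.

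**Working it through.** **Inputs.** Total n = 20 (STUDY SUMMARY), which agrees with 10 + 10 (STUDY ENDPOINTS, PROCEDURES INVOLVED). The criterion is 0 events. The plan gives no confidence level, acceptable rate, expected rate or dropout rate, so there is no figure of its own to reproduce. The two-sided 95% level is my assumption; the one-sided result is shown beside it.

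**Step 1: upper limit when no events are seen.** The exact (Clopper-Pearson) limit for 0/n is 1 − 0.025^(1/n) two-sided and 1 − 0.05^(1/n) one-sided.

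| Patients | Two-sided 95% | One-sided 95% |
|---|---|---|
| 0/20 | 1 − 0.025^(1/20) = 16.8% | 1 − 0.05^(1/20) = 13.9% |
| 0/10 | 1 − 0.025^(1/10) = 30.8% | 1 − 0.05^(1/10) = 25.9% |

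The Wilson limit for 0/20 is 16.1% and the rule of three gives 3/20 = 15.0%, so the choice of method does not matter. If fewer patients were evaluable (assumed), the two-sided exact limits would be 18.5% for 0/18, 20.6% for 0/16, 33.6% for 0/9 and 36.9% for 0/8.

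**Step 2: chance of meeting the criterion at an assumed true rate p.** This is (1 − p)^n.

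| True rate | None in 20 | None in 10 |
|---|---|---|
| 5% | 0.95^20 = 35.8% | 0.95^10 = 59.9% |
| 10% | 0.90^20 = 12.2% | 0.90^10 = 34.9% |

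**Step 3: the criterion in the other direction.** A single event of any cause fails it. At a 5% rate that happens with probability 1 − 0.358 = 64.2% in 20 patients. Yet 1/20 has an exact 95% interval of 0.1% to 24.9%, which overlaps almost entirely with the 0% to 16.8% from 0/20. The two results would be labelled as opposite outcomes although the data barely distinguish them.

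**Step 4: what the plan says about collecting events.** The Procedure Table has columns for light, biopsy, blood draw, survey and photographs, and none for adverse events. The table is not a full list of visit procedures: it has no PASI or dosimeter column, although the cohort descriptions require both throughout treatment. The absence of a column is therefore weak evidence by itself. The text outside the table also gives no definition, routine question, attribution or reporting step. The withdrawal rule requires someone to recognise adverse signs, but does not say how such a patient enters the safety result. The table's early-completion row is for resolved disease only.

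**The case against.** The strongest reply is that this is a small early study whose title calls it preliminary, using a device that the protocol describes as FDA approved with existing dermatological uses. The endpoint sits in a list with recruitment targets and user comfort, and has no test attached, so it may be a loosely worded goal and not a decision rule. That explains the wording, but it does not change what the sentence permits: no events, therefore safety demonstrated. Existing uses elsewhere do not settle safety in these two diseases, which the protocol itself chose to examine.

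A second reply is that harm would be noticed through session photographs, PASI scoring, the surveys, the dermatologist's oversight and the withdrawal rule, and that the CRFs may well hold an adverse-event field. This stands in part. A reader might infer from the Procedure Table that the study has no means of recording harm, or that nothing but light is given at the 8 of 15 treatment visits marked for light alone. The documents do not support either inference: the table is incomplete, the text requires photographs and dosimetry at each session, and the content of the CRFs is not given. What remains is narrower: the documents state no procedure for defining, eliciting, attributing or reporting events.

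**Conclusion.** The point holds in this form. As written, the endpoint supports a conclusion of demonstrated safety from data that, with no events, are compatible with a true per-patient rate of up to 16.8% overall and 30.8% in either cohort. It would also fail on one unrelated event, and the stated procedures do not let a reader tell absence from non-recording.

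The figures assume a two-sided 95% level, all 20 patients evaluable and, for the pooled figure, one common rate across two diseases. Recruitment is stated as at least 10 per cohort, so a larger sample would lower the limits somewhat; dropout would raise them. The one-sided limits lead to the same conclusion.

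A reader should not infer that the device is unsafe or that harm would go unseen. The documents show neither.

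**What to change.** Replace the safety endpoint with: *Estimate the proportion of patients with at least one adverse event, of any cause and separately those judged related to blue light, with exact two-sided 95% confidence intervals, by cohort and overall.*

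- **Denominator:** all patients who receive at least one session. Those withdrawn for adverse signs stay in it and count as events.
- **Listing:** show events by attributed cause: light, biopsy or blood draw, stopping of other treatment, concurrent standard phototherapy, other. The any-cause proportion keeps the result from resting on attribution alone.
- **Collection:** add a definition of an adverse event, and a short adverse-event question with attribution at each existing visit and at any exit from the study, whether by early completion, withdrawal or leaving for standard treatment.
- **Interpretation:** state in advance that 0/20 would exclude only rates above about 17% (0/10: about 31%) and that the safety result is preliminary.

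The cost is revised endpoint wording, one question and one attribution entry per visit, and an exit check; no added visits or patients. The downsides should be stated as limitations: a wide interval replaces a claim of demonstrated safety, attribution is unblinded, and effects arising after the last visit, including complications of the final biopsy, are not captured.

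### The comfort survey has no single stated timing, and patients who leave early for any reason other than resolution give at most a Visit 1 rating, which can bias the endpoint toward good tolerability

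*Combined protocol and SAP*

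**What the plan says.** All places are in the combined protocol and SAP.

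- **Study Endpoints, Objective 1:** the endpoint is "Obtain user comfort and experience with phototherapy system using psychometric survey". No time point, instrument or summary measure is given.
- **Procedures Involved, general visit text:** "During the first and last study visit the patient will be asked to complete surveys relating to their comfort and experience". The sentence goes on to cover the skin-symptom and quality-of-life surveys at the same two visits.
- **Procedures Involved, Procedure Table:** one column, "Psychometric and Skin QoL survey", is marked at Visit 1, Visit 15 and the row "Early completion (If condition resolved before final visit". Comfort has no column of its own.
- **Procedures Involved, Grover's and psoriasis narratives:** at baseline, "Patients will be asked to complete a baseline psychometric survey of skin-related symptoms and skin-related quality of life". Directly after the biopsy at 15 sessions comes "Patients will be asked to complete psychometric surveys relating to their comfort and experience with the phototherapy symptoms". Only the skin-symptom and quality-of-life surveys are said to be compared with baseline.
- **Withdrawal of Participants:** "If the patient shows adverse signs from the blue light therapy, they will be withdrawn from the study". Patients may also be withdrawn for not scheduling or attending sessions. Procedures Involved lets a patient leave at any time for standard-of-care treatment. No survey is specified on any of these three routes.

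**The concern.** The endpoint has no time point of its own, so the procedures text must supply one, and its parts do not line up. Staff working from the general visit text would give the comfort survey at Visit 1 and Visit 15. Staff working from a cohort narrative could reasonably give it once, at the end.

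The timing matters because comfort may itself influence who is still there to be asked. A patient withdrawn for adverse signs, or who stops attending because the sessions are unpleasant, is the patient whose rating is most needed, and the plan has no survey for that patient on leaving. If such patients are missing, or are represented only by a rating from the first day, the reported comfort can look better than the experience of everyone treated. A Visit 1 rating taken before any study light says nothing about the treatment at all.

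**Working it through.** The plan gives no figure to reproduce. The check is a comparison of the texts, a count of ratings by exit route, and an illustration under stated assumptions.

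**Step 1: timing in each place.**

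| Place | Comfort at Visit 1? | Comfort at end? |
|---|---|---|
| General visit text | Yes, explicit | Yes, explicit |
| Procedure Table | Merged column marked; comfort not named | Same |
| Grover's narrative | Not in the baseline survey | Listed after the final biopsy; no time stated |
| Psoriasis narrative | Not in the baseline survey | Listed after the final biopsy; no time stated |

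The table mark at Visit 1 fits either schedule, because the skin surveys alone would justify it.

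**Step 2: order within Visit 1.** The general text places the first biopsy and blood draw before the first session. For the surveys it says only that they occur during the visit, which the table labels as baseline. Before or after light is left open.

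**Step 3: comfort ratings per patient, by exit route.** The last column counts only ratings made after some exposure to study light.

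| Exit route | First and last visit | End only | First and last, if Visit 1 precedes light |
|---|---|---|---|
| Completes 15 sessions | 2 | 1 | 1 |
| Condition resolves early | 2 | 1 | 1 |
| Leaves after Visit 1 for adverse signs, non-attendance or standard of care | 1 | 0 | 0 |

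If the Visit 1 survey precedes light, the explicit schedule yields no more usable ratings than the end-only one. If it follows light, a leaver still contributes only a rating made after one session.

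**Step 4: illustration of size.** Assume a yes/no comfort rating, which the plan does not define, and w leavers in a cohort of 10, which the plan does not state. Let p be the proportion comfortable among those rated at the end and q the proportion among leavers.

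- End-only result: p.
- All treated: [(10 − w)p + wq] / 10.
- Difference: w(p − q) / 10.

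If leavers and stayers rate alike (p = q), the difference is 0. In the extreme case p = 1 and q = 0:

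| w | End only | All treated | Difference |
|---|---|---|---|
| 1 | 9/9 = 100% | 9/10 = 90% | 10 points |
| 2 | 8/8 = 100% | 8/10 = 80% | 20 points |
| 3 | 7/7 = 100% | 7/10 = 70% | 30 points |

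For w = 2, the exact (Clopper-Pearson) 95% lower limit is 0.025^(1/8) = 63.1% for 8/8, against 44.4% for 8/10. These are worst-case figures, not estimates.

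**The case against.** The strongest reply is that there is no true conflict. The general text is explicit, the table is compatible with it, and the narratives can be read as shorter summaries. Neither narrative says that comfort is asked only at the end. This stands in part. A reader might infer that the narratives schedule comfort solely after the last session, but that rests on sentence order. What remains is that both narratives run chronologically, specify the content of the baseline survey without comfort, and place comfort after the final biopsy. The two descriptions should be made to agree.

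A reader might also infer that comfort would be rated only by patients who tolerated the whole course. The documents do not support that. Patients whose condition resolves early are surveyed without finishing 15 sessions, and those who are missed include people leaving for scheduling reasons or for standard of care, who may have tolerated the light well.

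Nor is a first-to-last change in comfort at risk, since none is planned: only the skin surveys are compared with baseline. A survey about experience of phototherapy might also naturally be given after exposure, though the plan does not say so.

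Finally, this is one descriptive item in a 20-patient single-arm study, with no test or decision rule attached. That limits the consequences. It does not supply the missing ratings.

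**Conclusion.** The point holds in a limited form. The timing of the comfort survey is stated explicitly in one place and differently implied in two others, the table does not settle it, and the order relative to light at Visit 1 is unstated. Under either schedule, patients who leave for adverse signs, non-attendance or standard of care give at most a Visit 1 rating. This can bias an Objective 1 endpoint toward good tolerability.

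The direction assumes that those who leave are, on balance, less comfortable than those who stay. That is plausible for withdrawal on adverse signs but is not shown by the documents for the other routes. The size cannot be determined. The range of none to 10, 20 or 30 points for 1, 2 or 3 leavers per cohort depends on assumed dropout, an assumed yes/no rating and, at its upper end, complete separation of leavers from stayers. It should not be read as a prediction that the study would report 100% comfort.

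**What to change.** 1. Reconcile the general visit text with both cohort narratives so that the comfort survey's time points are stated once.
2. Split the table's survey column in two. At Visit 1, the DLQI and skin-symptom surveys come before light and the comfort survey comes after the first session. Repeat the comfort survey at Visit 15 or Early completion.
3. Offer the comfort survey at exit to any patient who leaves for another reason, and record that reason.
4. Report comfort for all patients with at least one session, by cohort, and show beside it the number who left before a final rating and why. Do not present a session-1 rating carried forward as an end-of-treatment rating: it cannot reflect discomfort that arose later.

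The cost is some rewording, one extra table column and one short questionnaire at exit. The general text already plans a Visit 1 survey, so no treatment visit is added. Some leavers may decline the exit survey, which is why the count of missing final ratings should be shown. The reported comfort may also be less favourable.
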